7.4.2. Contraception methods

Non-pregnant, non-breast-feeding women may be enrolled if they are considered highly unlikely to conceive. A highly effective method of birth control is defined as one that results in a low failure rate (i.e., less than 1 percent per year) when used consistently and correctly, such as implants, injectables, combined oral contraceptives, some intrauterine devices, sexual abstinence, or a vasectomized partner. For subjects using a hormonal contraceptive method, information regarding the product under evaluation and its potential effect on the

contraceptive should be addressed.

A female patient who is not of reproductive potential and therefore eligible to participate in this study without requiring the use of contraception is defined as: one who has either (1) reached natural menopause (defined as ≥ 6 months of spontaneous amenorrhea with serum follicle-stimulating hormone levels in the postmenopausal range as determined by the laboratory, or ≥ 12 months of spontaneous amenorrhea), or (2) ≥ 6 weeks post surgical hysterectomy, or bilateral oophorectomy with or without hysterectomy, or (3) bilateral tubal ligation.

The following are considered adequate barrier methods of contraception (including but not limited to): intrauterine device, diaphragm with spermicide, contraceptive sponge, condom, or vasectomy. For the purposes of this study, use of oral contraceptive pills are permitted but are not to be considered one of the two forms of birth control required. Patients should be informed that taking the study medication may involve unknown risks to the fetus (unborn baby) if pregnancy were to occur during the study and agree that in order to participate in the study they must adhere to the contraception requirement (described above) for the duration of the study.

7.5. Laboratory Evaluations

7.5.1 Clinical laboratory evaluations

Laboratory tests (including hematology, biochemistry, and urinalysis) will be scheduled as below. The examination items are included in **Table 7- 1**.

Lipid Profile: Blood samples to assess total cholesterol, triglycerides, HDL-C, LDL-C, LDL/HDL ratio will be obtained from visit 1 to visit 5.

Hematology: Blood samples to assess WBC, RBC, Hb, Hct, RDW, platelet, MCV, MCH, MCHC, neutrophil-band and segment, lymphocyte, monocyte, eosinophil, basophil will be obtained at visit 2 and visit 5.

Serum Biochemistry: Blood samples to assess AST, ALT, CPK, BUN and serum creatinine will be obtained from visit 2 to visit 5, albumin, total bilirubin, direct bilirubin, ALP, total protein will be obtained at visit 2 and visit 5. At screening visit, serum creatinine shall be run for estimating glomerular filtration rate (GFR).

Urinalysis: Assessments of urine pH, protein, glucose, ketone, blood, urobilinogen, bilirubin, nitrite, leukocyte and clinical microscopy will be tested at visit 2 and visit 5.

Pregnancy Test: Urine HCG test will be performed at visit 1.

12-lead ECG: ECG will be performed in accordance with the standard procedures at the site at visit 2 and visit 5.

baPWV and ABI measurement: baPWV is used to assess arterial stiffness and will be

obtained using VP 1000 or VP 1000 plus (Omron) at visit 2 and visit 5/early termination visit. ABI is a surrogate marker of atherosclerosis and will be obtained using the same device at visit 2 and visit 5/early termination visit.

Echocardiography: Values for S', E', and A' will be measured and averaged over three consecutive cardiac cycles. A composite mean for each of these parameters is then formed by taking the average of the values from the septal, lateral, and inferior wall. The ratio of the transmitral Doppler E wave velocity and the composite mean of E' will then be used to calculate the E/E' ratio. E/E' ratio will be obtained at visit 2 and visit 5.

CT scan of the liver: Each participant will undergo non-enhanced liver computed tomography (CT) scans at visit 2. The Hounsfield Unit (HU) attenuation of liver on CT scans will be utilized for determination of fatty liver (L/S ratio <1.0 and liver attenuation <40HU). Subjects who are confirmed with fatty liver will undergo liver CT scans again at visit 5.

Table 7- 1 Laboratory tests planned to be performed

Hematology	Biochemistry	Urinalysis	Others
WBC, RBC, Hb, Hct, RDW, platelet, MCV, MCH, MCHC, neutrophil band and segment, lymphocyte, monocyte, eosinophil, basophil	AST, ALT, CPK, BUN, serum creatinine, albumin, total bilirubin, direct bilirubin, ALP, total protein eGFR will be counted based on MDRD (Modification of Diet in Renal Disease) formulation: GFR (mL/min/1.73 m ²) = 186 x Scr -1.154 x Age -0.203 x 0.742 (if female)	pH, protein, glucose, ketone, blood, urobilinogen, bilirubin, nitrite, leukocyte, and clinical microscopy	Lipid Profile: total cholesterol, triglycerides, HDL-C, LDL-C, LDL/HDL ratio Biomarker: hsCRP, IL-1, IL-6, TNF- α

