4.3. Exclusion Criteria

Subjects are eligible if no exclusion criterion applies:

- (1) Patients with secondary dyslipidemia caused by diabetes mellitus, hypothyroidism, obstructive liver disease, chronic renal failure or drugs which can increase LDL-C level (e.g. retinoids, cyclosporine A and phenothiazines) or decrease HDL-C level (e.g. progestins, androgens, β -blockers, probucol and anabolic steroid)
- (2) Patients with lifestyle that may interfere treatment efficacy, such as alcoholism or drinking habits more than 3 times per week, late dinner, late night supper, frequent oversea business traveler, frequent social gathering, and patients who cannot anticipate a diet control and lifestyle changes;
- (3) Patients with diabetes or history of coronary artery disease (has had myocardial infarction, cardiac intervention, cerebrovascular accident/stroke or transient ischemic attack less than 6 months prior to Visit 1);
- (4) Patients with hypertension that is uncontrolled defined as 2 consecutive measurements of sitting blood pressure of systolic >140 mmHg or diastolic >90 mmHg at Visit 1;
- (5) Patient has a known hypersensitivity to Antroquinonol or related compounds;
- (6) Patient with uncontrolled intercurrent illness including, but not limited to, acute decompensated HF (exacerbation of chronic HF manifested by signs and symptoms that may require IV therapy), right heart failure due to severe pulmonary disease, diagnosed peripartum or chemotherapy induced cardiomyopathy within the 12 months prior to visit 1, or psychiatric illness/social situations that would limit compliance with study requirements;
- (7) Patients with a history of heart transplant or who are on a transplant list or with left ventricular assistance device (LVAD device);
- (8) Patients with documented ventricular arrhythmia with syncopal episodes within the past 3 months prior to visit 1 that remained untreated;
- (9) Patients with confirmed severe primary pulmonary, renal (eGFR <30 ml/min/1.73 m 2) or hepatic (Child-Pugh B/C classification) disease;
- (10) Patients who can't stop current lipid lowering drug treatments based on investigator's judgement;
- (11) Patients with any malignancy, treated or untreated, within the past 5 years of Visit 1 whether or not there is evidence of local recurrence or metastases, with the exception of localized basal cell carcinoma of the skin or carcinoma in situ of the cervix;

- (12) Female patient during pregnancy, lactation or breastfeeding;

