4.5.3. Subject identifier

Each subject will be assigned a consecutive numbers as he/she enters the study. In the study, the screening and randomization numbers are used as subject identifiers. The subject who signed the informed consent form will be assigned a sequential screening number starting with an alphabet "S" and following with 3 digits at visit 1 (Screening visit) by each site. The subject who meet the eligible criteria will be enrolled and granted a random number by randomization process before visit 2. The random number is composed of 3 digits and an initial alphabet "R". Once assigned to a subject, the screening numbers at each site and randomization numbers will not be reused. This random number will be used to identify the subject throughout the clinical study and must be used on all study documentation related to that subject. A two-digit site number will also be indicated on case report form as well as related working sheets. In that case, National Taiwan University Hospital will be coded as site "01". Once a new institution participates in the present study, the site number will be increased sequentially, e.g. site "02" for the second institution.

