6.2. Study Procedures

6.2.1. Screening (Day -14)

All patients must provide written informed consent before any study specific assessments or procedures are performed. A subject enrollment form documenting the investigator's assessment of each screened subject with regard to the protocol's inclusion and exclusion criteria has to be completed by the investigator.

Based on the results of Visit 1 assessments (see below 'Screening Assessments at Visit 1'), potentially eligible patients will enter a wash-out period as necessary. Blood test data generated by the study site or central laboratory 3 days prior to Visit 1 can be accepted.

Screening Assessments at Visit 1

- Demographics, medical history, including previous and concomitant diseases and treatments
- Physical examination
- Anthropometric measures (Height, Weight, Waist circumference, BMI)
- Vital signs (pulse rate, body temperature, respiratory rate, and blood pressure)
- Urine Pregnancy Test
- Blood samples for
 - lipid profile (total cholesterol, TG, HDL-C, LDL-C and LDL/HDL ratio)
 - biochemistry (serum creatinine for estimating GFR)

Patients will be instructed to come in fasted state for all subsequent study visits. Patients should receive information on a heart healthy diet and counseling on lifestyle changes as appropriate.

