7.5.2 Specimen preparation, handling, and storage

The blood and urine samples will be examined at Union Clinical Laboratory in line with the SOPs during the study. **The blood and urine samples will be examined at the site laboratory as well only for eligibility measurement at screening visit.**

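### No liver blood test is scheduled before randomisation, although two exclusions concern liver disease; disease that only a laboratory test would show can pass screening

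*Protocol*

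**What the plan says.** **The exclusions (Protocol section 4.3, repeated in SAP section 4.2.2).** Exclusion 1 begins "Patients with secondary dyslipidemia caused by diabetes mellitus, hypothyroidism, obstructive liver disease, chronic renal failure". Exclusion 9 covers confirmed severe pulmonary disease, renal disease (eGFR below 30) and "hepatic (Child-Pugh B/C classification) disease".

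**Screening.** The flow chart in section 6.1 marks the eligibility assessment at Visit 1 only. Apart from the lipid profile, section 6.2.1 lists one blood item: "biochemistry (serum creatinine for estimating GFR". Section 7.5.1 agrees: "At screening visit, serum creatinine shall be run for estimating glomerular filtration rate (GFR". Footnote 8 of the flow chart, in both the Protocol and SAP section 4.1.1, says the same. Visit 1 also includes a physical examination (sections 6.2.1 and 7.2) and a history review that names liver impairment and is checked against the exclusions (section 7.3).

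**First liver panel.** Section 7.5.1 states "Blood samples to assess AST, ALT, CPK, BUN and serum creatinine will be obtained from visit 2 to visit 5" and "albumin, total bilirubin, direct bilirubin, ALP, total protein will be obtained at visit 2 and visit 5". Visit 2 is Day 1, and section 6.2.2 has study drug given at that visit.

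**Randomisation.** Under section 4.5.1 the investigator confirms the criteria before contacting the randomisation centre. Section 4.5.3 says an eligible subject is "granted a random number by randomization process before visit 2", while sections 6.1 and 6.2.2 place randomisation at Visit 2.

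**Laboratories.** Section 7.5.2 sends samples to one named laboratory during the study. The site laboratory is used as well, but "only for eligibility measurement at screening visit".

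**The concern.** Exclusion 9 puts a renal and a hepatic condition in one sentence. The protocol schedules a screening blood test to support the renal one and none to support the hepatic one, nor the obstructive liver disease in exclusion 1. The tests that would inform both are already in the protocol, but they start at the visit where dosing starts.

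Two things are at stake. The first is safety: a patient with unrecognised liver impairment can be randomised and dosed before any protocol liver result has been looked at. The second is the analysis. Section 4.5.4(5) lists an eligibility violation not recognised at enrolment as a reason for discontinuation. Section 9.3 (SAP section 7.4.1) limits the ITT population to randomised patients who meet all criteria. A patient judged ineligible on Day 1 results would therefore be excluded after randomisation rather than counted as a screen failure.

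**Working it through.** The point rests on the order of events, and the plan states no figure to reproduce. Setting the sections side by side:

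| Step | What the documents schedule | Source |
|---|---|---|
| Visit 1 (Day -14) | Eligibility assessment, history, physical examination, lipids, creatinine | Protocol 6.1, 6.2.1, 7.2, 7.3, 7.5.1 |
| Random number | Before Visit 2, or at Visit 2 | Protocol 4.5.3; 6.1 and 6.2.2 |
| Visit 2 (Day 1) | First AST, ALT, ALP, bilirubin and albumin; first dose | Protocol 6.1 footnote 8, 6.2.2, 7.5.1 |
| Visit 3 (Day 29) | Next AST and ALT | Protocol 6.1, 6.2.3 |
| Visit 5 (Day 85) | Next ALP, bilirubin and albumin | Protocol 6.1 footnote 8, 6.2.3 |

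1. *Can a liver result be available before randomisation?* Footnote 3 in section 6.1 and section 6.2.2 let Visit 2 bloods be replaced by data from the 14 days before Visit 2. This needs three things: eligibility already confirmed, no wash-out required, and the investigator's agreement. It is optional and presupposes the eligibility decision. A patient on lipid-lowering drugs must have the two-week wash-out (section 4.2, criterion 3), so this route is closed and the documents give no other.

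2. *Must the Visit 2 result be reviewed before dosing?* No section says so. Even if randomisation takes place at Visit 2, there is no stated step at which the liver panel is read first.

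3. *Does the liver CT fill the gap?* It may be done between Visits 1 and 2, but section 7.5.1 gives its purpose as identifying fatty liver. It is not linked to exclusion 1 or 9.

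4. *What happens to a patient found ineligible late?* Section 4.5.4 allows discontinuation. Section 9.3 leaves the patient out of ITT, and out of PP because PP is a subset of ITT. The patient stays in the safety population if dosed.

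5. *Size per patient.* Enrolment is 120 / 4 = 30 per arm, so each loss is 1/30 = 3.3% of an arm. Section 9.2 allows 20% drop-out: 30 × 0.20 = 6 per arm, leaving 24, the stated minimum. Late-found ineligible patients use up that same allowance. How many there would be cannot be derived, because the documents give no rate of undetected liver disease.

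**The case against.** The strongest defence is that the liver exclusions are meant to be applied clinically. Exclusion 9 refers to confirmed disease. Its renal part is a laboratory number, so creatinine has to be run; its hepatic part is a clinical class. Exclusion 1 lists established causes, and Table 7-1 includes no thyroid test and no blood glucose, so the protocol relies on history for hypothyroidism and diabetes too. On this view the missing liver panel is a consistent design choice.

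Much of this stands, and it limits the point in four ways.

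- A reader might infer that hepatic exclusions come to light only after randomisation and dosing. The documents do not support that. History, physical examination and the investigator's confirmation of criteria (sections 4.5.1, 7.2 and 7.3) can find known or evident liver disease beforehand.
- A reader might infer that Visit 2 results always arrive after the first dose. Laboratory turnaround is not stated, and the sections disagree on whether the random number comes before or at Visit 2.
- An abnormal liver value is not in itself an eligibility violation. No section maps these analytes to a Child-Pugh class or to obstructive liver disease, and section 4.5.4 says subjects may, not must, be discontinued.
- The loss from ITT comes from the ITT definition and would follow any late-found ineligibility, not only hepatic.

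The defence does not remove the gap. History and examination cannot find disease that shows only in laboratory results. The comparison with thyroid and glucose testing is also incomplete: those would be new tests, whereas the liver analytes are already planned and only their first date is in question.

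**Conclusion.** The point holds in a limited form. Liver disease that only laboratory tests would show is not scheduled to be detected before randomisation, and for wash-out patients the documents provide no earlier liver panel. This follows from the schedule alone and needs no outside assumption.

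Its size is unknown. The number affected depends on how often such disease escapes history and examination, and on how many patients need wash-out; neither is given. A reader might be tempted to apply an assumed prevalence to the 120 patients and state a number lost, but nothing in the documents supports such a rate. What can be said is that each case costs 3.3% of an arm.

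Nor do the documents show bias in the treatment comparison. The Visit 2 sample is a baseline sample, so the likely harms are avoidable exposure and avoidable loss from both efficacy sets. This is an inexpensive improvement in patient safety and in keeping randomised patients in the analysis; it does not undermine the primary analysis.

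**What to change.** - In Protocol section 6.1 footnote 8, section 6.2.1 and section 7.5.1, and in SAP section 4.1.1 footnote 8, add AST, ALT, ALP, total and direct bilirubin and albumin to the Visit 1 blood sample.
- State that the investigator considers these results, together with history and examination, when judging the existing exclusions 1 and 9, and does so before the random number is issued. Add no cut-off; the criteria stay as written.
- Reconcile the timing of randomisation between section 4.5.3 (before Visit 2) and sections 6.1 and 6.2.2 (at Visit 2), so that it is clear what must be known at that moment.
- While editing footnote 8, reconcile two neighbouring inconsistencies. The Protocol footnote calls creatinine data from 3 days before Visit 1 unacceptable, while section 6.2.1 and the SAP footnote accept them. Section 7.5.1 ends biochemistry at Visit 5, while footnote 8 and section 6.2.4 continue to Visit 6.

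The cost is small: a few analytes on blood already drawn for creatinine, with no extra visit or draw, through a site-laboratory route that section 7.5.2 already provides for eligibility. The added expense falls mainly on screen failures and wash-out patients. For patients without wash-out, whose earlier bloods may already stand in for Visit 2, it is largely a change of date.

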7.5.2 Specimen preparation, handling, and storage

The blood and urine samples will be examined at Union Clinical Laboratory in line with the SOPs during the study. **The blood and urine samples will be examined at the site laboratory as well only for eligibility measurement at screening visit.**

7.6. Adverse event

The subject will be asked to report adverse event (AE) voluntarily and an investigator will also examine a subject for identifying adverse event at each visit during the study, starting from Visit 2 until the end of the trial. The methods and procedures for recording, assessing and reporting AEs are described in Section 8.

7.7. Concomitant medications

All concomitant medication used, either prescription or over-the-counter, and over-the-counter supplements (vitamins and herbal supplements) throughout the study period will be recorded.

8. ASSESSMENT OF SAFETY

8.1. Adverse Events (AE)

An adverse event is any untoward or unfavorable medical occurrence in a human subject, including any abnormal sign (for example, abnormal physical exam or laboratory finding), symptom, or disease, temporally associated with the subject's participation in the research, whether or not considered related to the subject's participation in the research.

All AEs including local and systemic reactions not meeting the criteria for "serious adverse events" will be captured on the appropriate AE page of CRF. Information to be collected includes event description, time of onset, clinician's assessment of severity, relationship to study product (assessed only by those with the training and authority to make a diagnosis) and time of resolution/stabilization of the event. All AEs occurring while on study must be documented appropriately regardless of relationship. All AEs will be followed to adequate resolution which means subjects experiencing AEs shall be followed until recovery, recovery with residual effects, continuing, death or lost to follow-up and be recorded on CRF AE page.

Pre-existing conditions will be recorded as baseline on the "Medical History" of CRF. If the pre-existing condition does not change, it does not have to be reported as an AE on subsequent cycles. However, if it deteriorates at any time during the study, it will be recorded as an AE.

All AEs must be graded for **severity** and **relationship** to study product. The adverse event toxicity grading scale used will be the CTCAE v4.03 grading score.

Severity of AEs

All AEs will be assessed by the clinician using a protocol defined grading system. For events not included in the protocol defined grading system, the following guidelines will be used to quantify intensity.

Grade 1	Mild; asymptomatic or mild symptoms; clinical or diagnostic observations only; intervention not indicated.
Grade 2	Moderate; minimal, local or noninvasive intervention indicated; limiting age-appropriate instrumental ADL.
Grade 3	Severe or medically significant but not immediately life-threatening; hospitalization or prolongation of hospitalization indicated; disabling; limiting self care ADL.
Grade 4	Life-threatening consequences; urgent intervention indicated
Grade 5	Death related to AE.

ADL: activities of Daily Living

Changes in the severity of an AE will be documented to allow an assessment of the duration of the event at each level of intensity to be performed. Adverse events characterized as intermittent require documentation of onset and duration of each episode.

Relationship to Study Drugs

The clinician's assessment of an AE's relationship to test article (study drug) is part of the documentation process, but it is not a factor in determining what is or is not reported in the study. If there is any doubt as to whether a clinical observation is an AE, the event will be reported. All AEs must have their relationship to study product assessed using the terms defined as follows. In a clinical trial, the study product must always be suspect. To help assess, the following guidelines are used.

Causality

- **Certain:** There is clear evidence to suggest a causal relationship, and other possible contributing factors can be ruled out. The clinical event, including an abnormal laboratory test result, occurs within a reasonable timeframe after study procedure(s) and cannot be explained by concurrent disease or other drugs or chemicals.
- **Probable:** There is evidence to suggest a causal relationship, and the influence of other factors is unlikely. The clinical event, including an abnormal laboratory test result, occurs within a reasonable time after study procedure(s), is unlikely to be attributed to concurrent disease or other drugs or chemicals, and follows a clinically reasonable response to study events.
- **Possible:** There is some evidence to suggest a causal relationship (e.g., the event occurred within a reasonable time after study procedure(s)). However, the influence of other factors may have contributed to the event (e.g., the subject's clinical condition, other concomitant events). Although an adverse event may be judged only as "possibly related" soon after discovery, it can be flagged as requiring more information and later be upgraded to "probably related" or "definitely related", as appropriate.
- **Unlikely:** A clinical event, including an abnormal laboratory test result, whose temporal relationship to study procedure(s) makes a causal relationship improbable (e.g., the event did not occur within a reasonable time after study procedure(s)) and in which other drugs or chemicals or underlying disease provides plausible explanations (e.g., the participant's clinical condition, other concomitant treatments).
- **Unrelated:** The AE is completely independent of study procedure(s), and/or evidence exists that the event is definitely related to another cause. There must be an alternative, definitive cause documented by the clinician.

